the initial point of defense from sexually transmitted infections. Interestingly, immune responses to AIDSVAX® B/E were higher after the initial boost than after the second boost 6 months later, suggesting that a delayed interval between priming and boosting may generate stronger immunity to booster vaccinations. Thus, boosting with a protein-based candidate HIV vaccine after a delay of several years can boost memory and elicit high magnitude immune responses in multiple compartments.

To further examine the impact of the interval between priming and boosting, the RV306 Phase II clinical trial was conducted in 360 healthy, unvaccinated participants to determine whether similar improvements in quality, magnitude or duration of humoral, cellular and mucosal responses could be afforded by boosting the RV144 regimen at either 12, 15, or 18 months post initial vaccination series, and to determine the optimal boosting interval for further clinical development. As with the primary RV144 vaccination series, boosting the RV144 vaccine regimen was safe overall, as there were no vaccine-related serious adverse events. Vaccination at month 12 with AIDSVAX® B/E with or without ALVAC, or at Month 15 or 18 with both vaccines, significantly improved humoral and cellular immunogenicity relative to participants who did not receive a late boost to the RV144 vaccine regimen. Overall, boosting at Month 15 or 18 resulted in stronger humoral and cellular responses than boosting at Month 12. Specifically, peak plasma IgG responses were higher in participants boosted at Month 15 or 18 than at Month 12 for all antigens. In addition, late boosting increased the durability of plasma IgG responses, as the median decrease of plasma IgG was 32-fold over 6 months without late boosting, but only 8-fold over 6 months in participants receiving late boost vaccinations. Longer boosting intervals also preferentially improved neutralization breadth. While vaccine boosts at any time point improved neutralization of the Tier 1 pseudoviruses MW965.26 (Subtype C); SF162.LS (Subtype B) and TH023.6 (Subtype AE), only boosting at Month 15 or Month 18 improved neutralization of subtype B MN.3.

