5.5. Missing Data

All attempts will be made to collect all data per protocol. No imputation will be performed for missing values. Outliers will not be excluded from the primary analyses but will be discussed in the analysis report. The number of non-missing values in each group will be described for all analyses.

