5.8. Multiple Comparisons/Multiplicity

For comparisons of safety outcomes, 5%-level two-sided tests will be made. Some of these may be implicit comparisons based on the overlap of group-level confidence intervals (i.e. non-overlapping 95% CIs mean rejecting the null hypothesis of no difference between groups at the 0.05-level).

To compare primary immunogenicity outcomes (antigen-specific plasma IgG binding responses, as measured by log AUC over time) across all groups, 5%-level two-sided tests will be used. When differences are found, pairwise comparisons between vaccination groups will be made using the Bonferroni-Holm step-down procedure [1] and a 5% significance threshold for the adjusted p-values; if no difference is found across all groups, no pairwise comparisons will be made. Collapsed comparisons will be considered separately and will be made with 2.5%-level two-sided tests, even when no pairwise differences are observed.

Further exploratory comparisons for immunogenicity endpoints across all groups will be adjusted for multiplicity by a Bonferroni adjustment: multiplying p-values by the number of assays in the same set (e.g. across antigens for a given antibody test; see Section 3.2.2 for sets of assays). Then a similar process as above will be followed, with pairwise comparisons following a significant overall test and Bonferroni-Holm step-down procedure (with a 5% significance level) to account for the multiple pairwise tests.

These adjustments are intended to improve control of the type-I error across comparisons for the same outcome measure and time point (e.g. Geometric Mean Titers (GMTs) for gp120A244 plasma IgG binding at Day 14) rather than across outcome measures and/or time. This level of type-I error control will still allow for exploratory findings that would be assessed further in future studies.

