8. IMMUNOGENICITY EVALUATION

8.1. Primary Immunogenicity Analysis

The primary immunogenicity endpoint is the magnitude of plasma IgG (antigen-specific) responses as measured by the endpoint titer, the same variable assessed in RV306. GMTs will be calculated for each group at each visit and the per-participant peak across all visits, along with 95% CIs (exponentiating the CI limits for the log GMT based on the normal distribution). Hypothesis testing is planned for targeted time points; this will be performed in order to aid in interpretation by helping to determine immune responses for potential further examination in future studies. First, group GMTs will be compared across all vaccination groups via ANOVA (null hypothesis that all groups share the same GMT) at the 5%-level, and if that is found to be significant, pairwise comparisons via 2-sided t-tests and the Bonferroni-Holm step-down procedure will be made and a 1% significance threshold will be applied. The two collapsed comparisons will be via 2-sided t-tests of log-GMTs at the $\alpha=0.025$ -level. If the data appear especially non-normal, nonparametric testing will be considered instead.

The reverse cumulative distribution (RCD) of titers (with endpoint titer on the x-axis and the proportion of participants with at least that titer on the y-axis) at each visit will be shown by vaccination group, separately for each antigen.

Seroconversion or seropositivity post-vaccination will be defined based on criteria given by the performing lab, and the number and percent of participants in each group achieving seroconversion/seropositivity at each visit will be presented along with the associated exact 95% Clopper-Pearson CI. The same group comparisons will be performed, via exact binomial tests and the same handling of significance and multiplicity.

Immune response over time (durability) will be assessed by the positive incremental area under the curve (AUC) based on a graph with log endpoint titer on the y-axis and visit day on the x-axis. For comparability between participants with different numbers of samples (visits) available, these values will be scaled by the week of the last available sample. If no sample is available for visits other than the first and last, no explicit imputation will be done, and the AUC will be calculated based on available samples. Log AUC will be analyzed similarly to the visit-by-visit titers.

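### The SAP's available-sample rule understates the durability AUC of any participant without a Day 14 titer, and scaling by the last week does not correct it

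*SAP*

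**What the plan says.** SAP 8.1 defines its durability measure as follows: "positive incremental area under the curve (AUC) based on a graph with log endpoint titer on the y-axis and visit day on the x-axis". To make participants with different numbers of samples comparable, "these values will be scaled by the week of the last available sample". For an interior gap the rule is "If no sample is available for visits other than the first and last, no explicit imputation will be done". The area is then taken from whichever titers remain. The result goes to formal testing: "Log AUC will be analyzed similarly to the visit-by-visit titers". SAP Tables 30 and 31 provide for pairwise and collapsed comparisons of log AUC.

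SAP 3.2.2.1 gives endpoint titer as the primary immunogenicity endpoint, but SAP 5.8 describes the primary outcomes as "antigen-specific plasma IgG binding responses, as measured by log AUC over time". SAP 5.5 adds the general rule "No imputation will be performed for missing values".

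Protocol 7.1.2 schedules humoral assays at Days 0, 14, 168 and 336. SAP 4.7 makes Day 336 only a possibility. Neither document names the integration rule, sets a minimum set of samples for the AUC, requires a Day 14 value, or plans a sensitivity analysis for incomplete AUCs.

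**The concern.** With at most four points on the curve, each carries much of the area. Day 14 is the only binding-antibody sample near the peak of the boost. If it is absent and the area comes from the remaining points, the curve runs directly from the Day 0 baseline to the decayed Day 168 value, and most of the early response drops out. The one adjustment in the plan, division by the week of the last sample, cannot help because the last sample is unchanged.

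At stake are the log-AUC tests across five groups and in the two collapsed contrasts, with 16 participants per group and 32 per collapsed arm. A few strongly distorted values can add noticeable variance at that size, even when the gaps occur at random.

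**Working it through.** **Plan's own figure.** The only figure given for the AUC is the detectable difference in SAP 4.4.1: 1.02 SD for 16 v 16, two-sided alpha 0.05, 80% power. A noncentral-t calculation gives 1.024 SD, so it reproduces. It assumes complete data; the plan has no figure for the effect of a missing sample.

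**Inputs.**
- Days 0, 14, 168, 336: Protocol 7.1.2; SAP 4.7 for the optional Day 336.
- Fall after a late boost in RV306: "only 8-fold over 6 months in participants receiving late boost vaccinations" (Protocol 5), which is log10(8) = 0.903.
- Increments in log10 titer above Day 0: p at Day 14, m = p − 0.903 at Day 168, e at Day 336.
- Assumptions, because the documents give neither: p from 1 to 3, and e between 0 and m.
- Linear trapezoid: assumed as the ordinary reading of an area on a graph.

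**Areas (log10 × days).**
- All four visits: 7p + 77(p + m) + 84(m + e) = 84p + 161m + 84e.
- Day 14 missing: 84m + 84(m + e) = 168m + 84e. Change: −(84p − 7m).
- Day 168 missing: 7p + 161(p + e) = 168p + 161e. Change: 84p − 161m + 77e.
- Day 168 last: complete 84p + 77m; Day 14 missing 84m. Change: again −(84p − 7m).

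The Day 14 change is a loss for any response that peaks at Day 14. With no decline at all (p = m = e) it is 77/329 = 23%. Scaling divides the complete and the incomplete area by the same week (48 or 24), so these percentages are unchanged by it.

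**Worked case: p = 1.5, m = 0.597, e = m/2.**

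| Record | Area | Change |
|---|---|---|
| Four visits, complete | 247.2 | |
| Day 14 missing | 125.4 | −49% |
| Day 168 missing | 300.1 | +21% |
| Ending Day 168, complete | 172.0 | |
| Ending Day 168, Day 14 missing | 50.1 | −71% |

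**Range over p = 1 to 3 and e = 0 to m.**
- Day 14 missing, four visits: 99.6 to 16.3 (−84%) at p = 1, e = 0; 765.7 to 528.4 (−31%) at p = 3, e = m.
- Day 14 missing, Day 168 last: −91% at p = 1; −57% at p = 3.
- Day 168 missing: +70% at p = 1, e = m; −15% at p = 3, e = 0. It is exactly zero if the decline from Day 14 to Day 336 is linear.

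**Effect on a group mean.** In the worked case one participant's log10 AUC moves by log10(125.4/247.2) = −0.29 (four visits), or −0.54 if Day 168 is last. One such participant in 16 moves the group mean by about −0.02 or −0.03.

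**Effect on the test.** Simulation of the log-AUC t-test, 32 v 32, two-sided 0.025. Assumed: worked-case means, increment SD 0.5, correlation 0.6, true shift 0.35 log10, scaled AUC floored at 0.1 so that the log exists, and Day 14 missing at random.

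| AUC ends | Day 14 titers missing, of 64 | Power, SAP rule | Power, AUC set to missing |
|---|---|---|---|
| Day 168 | 1 | 65% | 71% |
| Day 168 | 3 | 58% | 70% |
| Day 336 | 3 | 74% | 77% |

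These are approximate. A repeat run came within about two percentage points of each.

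**The case against.** The case on the other side has real substance.

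- **Gaps may be rare.** In RV306, 274 of 300 active late-boost recipients (91.3%) had all vaccinations and visits (Protocol 5.9). Withdrawals up to 30 days after injection may be replaced (Protocol 8.6.3). Leukapheresis participants still have plasma stored at Day 14 (Protocol Table 3, footnote 4). The documents give no missing rate, so the practical cost is unknown. This stands.
- **Other analyses do not bridge gaps.** The visit-by-visit GMTs and the GEE model in SAP 8.2 use observed titers, nonparametric tests are available, and the study calls itself exploratory. This stands and limits the damage. It does not remove it, because SAP 5.8 names log AUC in describing the primary comparison.
- **The trapezoid is inferred.** True. If another rule is intended, the SAP should name it.

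Some stronger readings are tempting but not supported:

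- A reader might infer that SAP 8.1 contradicts SAP 5.5. It does not: 8.1 disclaims only explicit imputation and openly accepts working from available points.
- A reader might take the worked-case percentages as the expected error. They depend on an assumed trajectory, and −49% and −71% belong to different visit schedules.
- A reader might infer that losing Day 168 inflates the AUC by about a fifth. The sign depends on whether the true Day 168 value lies below or above the line from Day 14 to Day 336. If Day 336 is not assayed, Day 168 is the last visit and the case does not arise.
- A reader might infer that affected participants look like non-responders, or that one group is favoured. In the worked case the AUC to Day 336 is halved, not abolished. Contrasts are pushed toward one group only if missingness differs between groups.

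**Conclusion.** The concern holds for Day 14. Under straight-line joining, a missing Day 14 titer always understates the AUC of a response that peaks there, and the planned scaling leaves the error in place. The size is about 31% to 84% with Day 336 assayed and 57% to 91% if Day 168 is last, given the RV306 8-fold fall, an assumed rise of 1 to 3 log10, and an assumed Day 336 value between baseline and the Day 168 level. For Day 168 the only supportable statement is that the AUC can move either way, by about −15% to +70%, and only when Day 336 is assayed.

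With random missingness the consequence is mainly added variance and diluted contrasts. Under the simulation's assumptions, three missing Day 14 titers among 64 cost about 12 points of power relative to setting those AUCs to missing (58% v 70%) when the AUC ends at Day 168, and about 3 points (74% v 77%) when it ends at Day 336. The change is worth making because it costs almost nothing, not because the trial's conclusions are known to be at risk.

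**What to change.** In SAP 8.1:

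1. Name the rule: linear trapezoid on log titer above baseline.
2. Replace the sentence on missing interior samples with: *AUC is calculated only if the Day 0 and Day 14 titers and at least one later titer are available; otherwise it is set to missing.*
3. Add a sensitivity analysis of log AUC restricted to participants with all scheduled binding-antibody samples. This also covers the Day 168 gap, which the new sentence still allows.

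The planned GEE is not a ready substitute for the third step. As specified in SAP 8.2 and Table 35 it has no placebo term, and a weighted sum of its visit means is neither a positive incremental AUC nor a log AUC.

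Cost: a wording change and one extra analysis. A few participants leave the AUC test; the visit-by-visit GMTs are unaffected.

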8.2. Additional Immunogenicity Analyses

Further immunogenicity analyses (see Section 3.2.2 for planned sets of assays) will be considered exploratory for testing purposes (see Section 5.8 for how significance and multiplicity will be handled), but they will otherwise follow a similar process as the primary immunogenicity analysis. For assays that are not conducted via titer experiments, the analysis values will be handled as log GMTs are, after appropriate transformation of the data to be

approximately normal when necessary; instead of RCD curves, boxplots will show the assay values for each group, by visit.

The kinetics of log IgG titers over time will be assessed via generalized estimating equations (GEE) models, with the immune response appropriately-transformed to assume normally-distributed error terms and RV546 vaccine dosage, adjuvant, study day, and all 2- and 3-way interactions included as covariates. These covariates will be assessed for significance at the 1%-level, and any findings will be considered hypothesis-generating. An unstructured working covariance matrix will be preferred, but other choices may be necessary due to computational challenges or poor model fit. These details will be described in the final report. Similar models may be fit for other assays, and these would also be considered exploratory.

To assess the relationship between possible confounders and the appropriately-transformed titers at the primary endpoint time point, a linear regression model will be fit as well, adjusting for vaccination group, age, sex, RV306 vaccination group, and time between final RV306 vaccination and RV546 vaccination. Covariates will be assessed for significance at the 1%-level, and again findings will be considered hypothesis-generating. Similar models may be fit for other assays also.

9. REPORTING CONVENTIONS

P-values ≥ 0.001 and ≤ 0.999 will be reported to 3 decimal places; p-values less than 0.001 will be reported as “ <0.001 ”. The mean, standard deviation, and other statistics will be reported to one decimal place beyond the analysis data. The minimum and maximum will use the same number of decimal places as the analysis data. Proportions will be presented as two decimal places; values greater than zero but less than 0.01 will be presented as “ <0.01 ”. Percentages will be reported to the nearest whole number; values greater than zero but less than 1% will be presented as “ <1 ”; values greater than 99% but less than 100% will be reported as “ $>99\%$ ”. Estimated parameters, not on the same scale as raw observations (e.g. regression coefficients) will be reported to 3 significant figures.

10. TECHNICAL DETAILS

SAS version 9.4 or above and R version 3.6 or above will be used to generate all tables, figures, and listings. Other software may be used for processing of assays, and further details will be presented in the final report if they are available.

13. LISTING OF TABLES, FIGURES, AND LISTINGS

Table, figure, and listing shells are presented in Appendices 1, 2, and 3.

APPENDICES

Participant Disposition	Full IHV01/A244 (N=X)		Fractional IHV01/A244 (N=X)		Full IHV01/A244 + ALFQ (N=X)		Fractional IHV01/A244 + ALFQ (N=X)		Placebo (N=X)		All Participants (N=X)	
	n	%	n	%	n	%	n	%	n	%	n	%
Screened	--	--	--	--	--	--	--	--	--	--	x	--
Enrolled/Randomized	x	100	x	100	x	100	x	100	x	100	x	100
Received Study Vaccination (Visit 1, Day 0)	x	xx	x	xx	x	xx	x	xx	x	xx	x	xx
Completed Visit 2 (Day 1)	x	xx	x	xx	x	xx	x	xx	x	xx	x	xx
Completed Visit 3 (Day 7)	x	xx	x	xx	x	xx	x	xx	x	xx	x	xx
Completed Visit 4 (Day 14)	x	xx	x	xx	x	xx	x	xx	x	xx	x	xx
Completed Visit 5 (Day 168)	x	xx	x	xx	x	xx	x	xx	x	xx	x	xx
Completed Follow-up (Visit 6, Day 336)	x	xx	x	xx	x	xx	x	xx	x	xx	x	xx
Completed All Scheduled Blood Draws	x	xx	x	xx	x	xx	x	xx	x	xx	x	xx

Note: N = Number of randomized participants

Table 6: Summary of Categorical Demographic and Baseline Characteristics by Site

Variable	Characteristic	[Site 1] (N=X)		[Site 2] (N=X)		All Participants (N=X)		p-value
		n	%	n	%	n	%	
Age	20-29	x	xx	x	xx	x	xx	0.xx
	30-39							-
	40-49							-
	50+							-
Sex	Male							0.xx
	Female							-
Level of Education	Primary school							0.xx
	Secondary school							-
	Vocational							-
	Bachelor degree							-
	Higher than bachelor degree							-
Occupation	No occupation							0.xx
	Student							-
	Government employee							-
	Private sector employee							-
	Merchant/Self-employed							-
	Agriculturist/Farmer							-
	Other							-
Note: N = Number of randomized participants. Exact binomial test used to compare variables between sites.								

Table 7: Summary of Continuous Demographic and Baseline Characteristics by Site

Variable	Statistic	[Site 1] (N=X)	[Site 2] (N=X)	All Participants (N=X)	p-value
Age	Mean	xx	xx	xx	0.xx
	Standard Deviation	xx	xx	xx	-
	Median	xx	xx	xx	-
	Minimum	x	x	x	-
BMI	Maximum	x	x	x	-
	Mean	xx	xx	xx	0.xx
	Standard Deviation	xx	xx	xx	-
	Median	xx	xx	xx	-
	Minimum	x	x	x	-
	Maximum	x	x	x	-
Note: N = Number of randomized participants. t-test used to compare variables between sites.					

Table 8: Summary of Categorical Demographic and Baseline Characteristics by Vaccination Group

Variable	Statistic	Full IHV01/A244 (N=X)		Fractional IHV01/A244 (N=X)		Full IHV01/A244 + ALFQ (N=X)		Fractional IHV01/A244 + ALFQ (N=X)		Placebo (N=X)		All Participants (N=X)	
		n	%	n	%	n	%	n	%	n	%	n	%
Age	20-29	x	xx	x	xx	x	xx	x	xx	x	xx	x	xx
	30-39												
	40-49												
	50+												
Sex	Male												
	Female												
Level of Education	Primary school												
	Secondary school												
	Vocational												
	Bachelor degree												
	Higher than bachelor degree												
Occupation	No occupation												
	Student												
	Government employee												
	Private sector employee												
	Merchant/Self-employed												
	Agriculturist/Farmer												
	Other												
Note: N = Number of randomized participants													

Table 9: Summary of Continuous Demographic and Baseline Characteristics by Vaccination Group

Variable	Characteristic	Full IHV01/A244 (N=X)		Fractional IHV01/A244 (N=X)		Full IHV01/A244 + ALFQ (N=X)		Fractional IHV01/A244 + ALFQ (N=X)		Placebo (N=X)		All Participants (N=X)	
		n	%	n	%	n	%	n	%	n	%	n	%
Age	Mean	x	xx	x	xx	x	xx	x	xx	x	xx	x	xx
	Standard Deviation												
	Median												
	Minimum												
	Maximum												
BMI	Mean												
	Standard Deviation												
	Median												
	Minimum												
	Maximum												
Note: N = Number of randomized participants													

Table 10: Summary of Participants with Pre-Existing Medical Conditions by MedDRA System Organ Class and Vaccination Group

MedDRA System Organ Class	Full IHV01/A244 (N=X)		Fractional IHV01/A244 (N=X)		Full IHV01/A244 + ALFQ (N=X)		Fractional IHV01/A244 + ALFQ (N=X)		Placebo (N=X)		All Participants (N=X)	
	n	%	n	%	n	%	n	%	n	%	n	%
Any SOC	x	X.X	x	X.X	x	X.X	x	X.X	x	X.X	x	X.X
[SOC 1]	x	X.X	x	X.X	x	X.X	x	X.X	x	X.X	x	X.X
[SOC 2]												

Note: N = Number of randomized participants; n = Number of participants reporting medical history within the specified SOC. A participant is only counted once per SOC.

Table 11: Distribution of Protocol Deviations by Category, Type, and Vaccination Group

Category	Deviation Type	Full IHV01/A244 (N=X)		Fractional IHV01/A244 (N=X)		Full IHV01/A244 + ALFQ (N=X)		Fractional IHV01/A244 + ALFQ (N=X)		Placebo (N=X)		All Participants (N=X)	
		No. of Part.	No. of Dev.	No. of Part.	No. of Dev.	No. of Part.	No. of Dev.	No. of Part.	No. of Dev.	No. of Part.	No. of Dev.	No. of Part.	No. of Dev.
Eligibility/enrollment	Any type	x	x	x	x	x	x	x	x	x	x	x	x
	Did not meet inclusion criterion	x	x	x	x	x	x	x	x	x	x	x	x
	Met exclusion criterion	x	x	x	x	x	x	x	x	x	x	x	x
	ICF not signed prior to study procedures	x	x	x	x	x	x	x	x	x	x	x	x
	Other	x	x	x	x	x	x	x	x	x	x	x	x
Follow-up visit schedule	Any type	x	x	x	x	x	x	x	x	x	x	x	x
	Out of window visit	x	x	x	x	x	x	x	x	x	x	x	x
	Missed visit/visit not conducted	x	x	x	x	x	x	x	x	x	x	x	x
	Other	x	x	x	x	x	x	x	x	x	x	x	x
Protocol procedure/assessment	Any type	x	x	x	x	x	x	x	x	x	x	x	x
	Incorrect version of ICF signed	x	x	x	x	x	x	x	x	x	x	x	x
	Blood not collected	x	x	x	x	x	x	x	x	x	x	x	x
	Urine not collected	x	x	x	x	x	x	x	x	x	x	x	x
	[Insert other deviation types observed]	x	x	x	x	x	x	x	x	x	x	x	x
	Other	x	x	x	x	x	x	x	x	x	x	x	x
Vaccine administration	Any type	x	x	x	x	x	x	x	x	x	x	x	x
	Required procedure done incorrectly	x	x	x	x	x	x	x	x	x	x	x	x
	Study product temperature excursion	x	x	x	x	x	x	x	x	x	x	x	x
	Other	x	x	x	x	x	x	x	x	x	x	x	x
Blinding policy/procedure	Any type	x	x	x	x	x	x	x	x	x	x	x	x
	Study assignment unblinded	x	x	x	x	x	x	x	x	x	x	x	x
	Other	x	x	x	x	x	x	x	x	x	x	x	x

Note: N = Number of participants enrolled

Note: Example categories and deviation types given

Table 12: DAIDS Table for Grading the Severity of Adverse Events

See: <https://rsc.niaid.nih.gov/sites/default/files/daidsgradingcorrectedv21.pdf>

SAFETY SUMMARY

Table 13: Overall Summary of Adverse Events

	Full IHV01/A244 (N=X)		Fractional IHV01/A244 (N=X)		Full IHV01/A244 + ALFQ (N=X)		Fractional IHV01/A244 + ALFQ (N=X)		Placebo (N=X)		All Participants (N=X)	
Participants ^a with	n	%	n	%	n	%	n	%	n	%	n	%
At least one local solicited adverse event	x	x.x	x	x.x	x	x.x	x	x.x	x	x.x	x	x.x
Mild (Grade 1)												
Moderate (Grade 2)												
Severe (Grade 3)												
At least one systemic solicited adverse event	x	x.x	x	x.x	x	x.x	x	x.x	x	x.x	x	x.x
Mild (Grade 1)												
Moderate (Grade 2)												
Severe (Grade 3)												
At least one unsolicited adverse event	x	x.x	x	x.x	x	x.x	x	x.x	x	x.x	x	x.x
At least one related unsolicited adverse event	x	x.x	x	x.x	x	x.x	x	x.x	x	x.x	x	x.x
Mild (Grade 1)	x	x.x	x	x.x	x	x.x	x	x.x	x	x.x	x	x.x
Moderate (Grade 2)	x	x.x	x	x.x	x	x.x	x	x.x	x	x.x	x	x.x
Severe (Grade 3)	x	x.x	x	x.x	x	x.x	x	x.x	x	x.x	x	x.x
At least one severe (Grade 3) unsolicited adverse event	x	x.x	x	x.x	x	x.x	x	x.x	x	x.x	x	x.x
Related	x	x.x	x	x.x	x	x.x	x	x.x	x	x.x	x	x.x
Unrelated	x	x.x	x	x.x	x	x.x	x	x.x	x	x.x	x	x.x
At least one adverse event of special interest	x	x.x	x	x.x	x	x.x	x	x.x	x	x.x	x	x.x
At least one serious adverse event ^b	x	x.x	x	x.x	x	x.x	x	x.x	x	x.x	x	x.x
At least one related, serious adverse event	x	x.x	x	x.x	x	x.x	x	x.x	x	x.x	x	x.x
At least one adverse event leading to early termination	x	x.x	x	x.x	x	x.x	x	x.x	x	x.x	x	x.x
N = Number of participants in the Safety Population												
^a Participants are counted once for each category regardless of the number of events.												
^b See listing of Serious Adverse Events												

Table 14: Adverse Events Occurring in 5% of Participants in Any Vaccination Group by MedDRA System Organ Class and Preferred Term, and Vaccination Group

MedDRA System Organ Class	MedDRA Preferred Term	Full IHV01/A244 (N=X)			Fractional IHV01/A244 (N=X)			Full IHV01/A244 + ALFQ (N=X)			Fractional IHV01/A244 + ALFQ (N=X)			Placebo (N=X)			All Participants (N=X)		
		n	%	Events	n	%	Events	n	%	Events	n	%	Events	n	%	Events	n	%	Events
Serious Adverse Events																			
All	All	x	x.x	x	x	x.x	x	x	x.x	x	x	x.x	x	x	x.x	x	x	x.x	x
SOC1	PT1	x	x.x	x	x	x.x	x	x	x.x	x	x	x.x	x	x	x.x	x	x	x.x	x
Etc.	Etc.																		
Other (Non-Serious) Adverse Events																			
All	All	x	x.x	x	x	x.x	x	x	x.x	x	x	x.x	x	x	x.x	x	x	x.x	x
SOC1	PT1	x	x.x	x	x	x.x	x	x	x.x	x	x	x.x	x	x	x.x	x	x	x.x	x
Etc	Etc																		
Solicited Adverse Events																			
All	All	x	x.x	x	x	x.x	x	x	x.x	x	x	x.x	x	x	x.x	x	x	x.x	x
SOC1	PT1	x	x.x	x	x	x.x	x	x	x.x	x	x	x.x	x	x	x.x	x	x	x.x	x
Etc	Etc																		
Clinical Laboratory Adverse Events																			
All	All	x	x.x	x	x	x.x	x	x	x.x	x	x	x.x	x	x	x.x	x	x	x.x	x
SOC1	PT1	x	x.x	x	x	x.x	x	x	x.x	x	x	x.x	x	x	x.x	x	x	x.x	x
Etc	Etc																		
Note: N = Number of participants in the Safety Population; n = Number of participants reporting event; Events = Total frequency of events reported.																			

Table 15: Collapsed Comparisons of the Proportion of Participants Experiencing Adverse Events by Event Type

Event Type	Full IHV01/A244 (N=X)	Fractional IHV01/A244 (N=X)	p-value ^a	Any ALFQ (N=X)	No ALFQ (N=X)	p-value ^a
	n (%)	n (%)		n (%)	n (%)	
Solicited Adverse Events						
Any Solicited Symptom	x (x.x)	x (x.x)	0.xx	x (x.x)	x (x.x)	0.xx
Moderate (Grade 2) ^b	x (x.x)	x (x.x)	0.xx	x (x.x)	x (x.x)	0.xx
Severe (Grade 3) ^b	x (x.x)	x (x.x)	0.xx	x (x.x)	x (x.x)	0.xx
Any Systemic Symptom	x (x.x)	x (x.x)	0.xx	x (x.x)	x (x.x)	0.xx
Moderate (Grade 2) ^b	x (x.x)	x (x.x)	0.xx	x (x.x)	x (x.x)	0.xx
Severe (Grade 3) ^b	x (x.x)	x (x.x)	0.xx	x (x.x)	x (x.x)	0.xx
Any Local Symptom	x (x.x)	x (x.x)	0.xx	x (x.x)	x (x.x)	0.xx
Moderate (Grade 2) ^b	x (x.x)	x (x.x)	0.xx	x (x.x)	x (x.x)	0.xx
Severe (Grade 3) ^b	x (x.x)	x (x.x)	0.xx	x (x.x)	x (x.x)	0.xx
Unsolicited Adverse Events						
Any Serious Adverse Event	x (x.x)	x (x.x)	0.xx	x (x.x)	x (x.x)	0.xx
Any Adverse Event of Special Interest	x (x.x)	x (x.x)	0.xx	x (x.x)	x (x.x)	0.xx
Any Related, Unexpected Adverse Event	x (x.x)	x (x.x)	0.xx	x (x.x)	x (x.x)	0.xx
Any Unexpected Adverse Event Within 28 Days of Study Vaccination	x (x.x)	x (x.x)	0.xx	x (x.x)	x (x.x)	0.xx
Note: N = Number of participants in the Safety Population; n = Number of participants reporting each symptom						
^a Exact binomial tests used						
^b Maximum severity reported						

SOLICITED ADVERSE EVENTS

Table 16: Number and Percentage of Participants Experiencing Solicited Reactogenicity Events with 95% Confidence Intervals, by Event and Vaccination Group

Event	Full IHV01/A244 (N=X)			Fractional IHV01/A244 (N=X)			Full IHV01/A244 + ALFQ (N=X)			Fractional IHV01/A244 + ALFQ (N=X)			Placebo (N=X)			All Participants (N = X)		
	n	%	95% CI	n	%	95% CI	n	%	95% CI	n	%	95% CI	n	%	95% CI	n	%	95% CI
Any Reactogenicity	x	x.x	x.x, x.x	x	x.x	x.x, x.x	x	x.x	x.x, x.x	x	x.x	x.x, x.x	x	x.x	x.x, x.x	x	x.x	x.x, x.x
Any Systemic Reactogenicity	x	x.x	x.x, x.x	x	x.x	x.x, x.x	x	x.x	x.x, x.x	x	x.x	x.x, x.x	x	x.x	x.x, x.x	x	x.x	x.x, x.x
[Systemic Event 1]	x	x.x	x.x, x.x	x	x.x	x.x, x.x	x	x.x	x.x, x.x	x	x.x	x.x, x.x	x	x.x	x.x, x.x	x	x.x	x.x, x.x
[Systemic Event 2]	x	x.x	x.x, x.x	x	x.x	x.x, x.x	x	x.x	x.x, x.x	x	x.x	x.x, x.x	x	x.x	x.x, x.x	x	x.x	x.x, x.x
Any Local Reactogenicity	x	x.x	x.x, x.x	x	x.x	x.x, x.x	x	x.x	x.x, x.x	x	x.x	x.x, x.x	x	x.x	x.x, x.x	x	x.x	x.x, x.x
[Local Event 1]	x	x.x	x.x, x.x	x	x.x	x.x, x.x	x	x.x	x.x, x.x	x	x.x	x.x, x.x	x	x.x	x.x, x.x	x	x.x	x.x, x.x
[Local Event 2]	x	x.x	x.x, x.x	x	x.x	x.x, x.x	x	x.x	x.x, x.x	x	x.x	x.x, x.x	x	x.x	x.x, x.x	x	x.x	x.x, x.x
Note: N = Number of participants in the Safety Population																		

Tables with similar format:

Table 17: Number and Percentage of Male Participants Experiencing Solicited Reactogenicity Events with 95% Confidence Intervals, by Event and Vaccination Group

Table 18: Number and Percentage of Female Participants Experiencing Solicited Reactogenicity Events with 95% Confidence Intervals, by Event and Vaccination Group

Table 19: Number and Percentage of Participants Experiencing Solicited Reactogenicity Events by Event, Maximum Severity, and Vaccination Group

Event	Severity	Full IHV01/A244 (N=X)		Fractional IHV01/A244 (N=X)		Full IHV01/A244 + ALFQ (N=X)		Fractional IHV01/A244 + ALFQ (N=X)		Placebo (N=X)	
		n	%	n	%	n	%	n	%	n	%
Any Reactogenicity	None	X	X.X	X	X.X	X	X.X	X	X.X	X	X.X
	Mild	X	X.X	X	X.X	X	X.X	X	X.X	X	X.X
	Moderate	X	X.X	X	X.X	X	X.X	X	X.X	X	X.X
	Severe	X	X.X	X	X.X	X	X.X	X	X.X	X	X.X
Systemic Reactogenicity											
Any Systemic Reactogenicity	None	X	X.X	X	X.X	X	X.X	X	X.X	X	X.X
	Mild	X	X.X	X	X.X	X	X.X	X	X.X	X	X.X
	Moderate	X	X.X	X	X.X	X	X.X	X	X.X	X	X.X
	Severe	X	X.X	X	X.X	X	X.X	X	X.X	X	X.X
[Systemic Event 1]	None	X	X.X	X	X.X	X	X.X	X	X.X	X	X.X
	Mild	X	X.X	X	X.X	X	X.X	X	X.X	X	X.X
	Moderate	X	X.X	X	X.X	X	X.X	X	X.X	X	X.X
	Severe	X	X.X	X	X.X	X	X.X	X	X.X	X	X.X
[Systemic Event 2]	None	X	X.X	X	X.X	X	X.X	X	X.X	X	X.X
	Mild	X	X.X	X	X.X	X	X.X	X	X.X	X	X.X
	Moderate	X	X.X	X	X.X	X	X.X	X	X.X	X	X.X
	Severe	X	X.X	X	X.X	X	X.X	X	X.X	X	X.X
Local Reactogenicity											
Any Local Reactogenicity	None	X	X.X	X	X.X	X	X.X	X	X.X	X	X.X
	Mild	X	X.X	X	X.X	X	X.X	X	X.X	X	X.X
	Moderate	X	X.X	X	X.X	X	X.X	X	X.X	X	X.X
	Severe	X	X.X	X	X.X	X	X.X	X	X.X	X	X.X
[Local Event 1]	None	X	X.X	X	X.X	X	X.X	X	X.X	X	X.X
	Mild	X	X.X	X	X.X	X	X.X	X	X.X	X	X.X
	Moderate	X	X.X	X	X.X	X	X.X	X	X.X	X	X.X
	Severe	X	X.X	X	X.X	X	X.X	X	X.X	X	X.X
[Local Event 2]	None	X	X.X	X	X.X	X	X.X	X	X.X	X	X.X
	Mild	X	X.X	X	X.X	X	X.X	X	X.X	X	X.X
	Moderate	X	X.X	X	X.X	X	X.X	X	X.X	X	X.X
	Severe	X	X.X	X	X.X	X	X.X	X	X.X	X	X.X
Note: N = Number of participants in the Safety Population who received the specified dose; n = Number of participants reporting each event; severity is the maximum severity reported post dosing for each participant for each day.											

Tables with similar format to Table 19:

Table 20: Number and Percentage of Male Participants Experiencing Solicited Reactogenicity Events by Event, Maximum Severity, and Vaccination Group

Table 21: Number and Percentage of Female Participants Experiencing Solicited Reactogenicity Events by Event, Maximum Severity, and Vaccination Group

UNSOLICITED ADVERSE EVENTS

Table 22: Summary of Unsolicited Adverse Events by MedDRA System Organ Class and Preferred Term, and Vaccination Group

MedDRA® System Organ Class	MedDRA® Preferred Term	Full IHV01/A244 (N=X)				Fractional IHV01/A244 (N=X)				Full IHV01/A244 + ALFQ (N=X)				Fractional IHV01/A244 + ALFQ (N=X)				Placebo (N=X)			
		n	%	95% CI	Events	n	%	95% CI	Events	n	%	95% CI	Events	n	%	95% CI	Events	n	%	95% CI	Events
Serious Adverse Events																					
Any SOC	Any PT	x	x.x	x.x, x.x	x	x	x.x	x.x, x.x	x	x	x.x	xx, xx	x	x	x.x	xx, xx	x	x	x.x	xx, xx	x
[SOC 1]	Any PT	x	x.x	x.x, x.x	x	x	x.x	x.x, x.x	x	x	x.x	xx, xx	x	x	x.x	xx, xx	x	x	x.x	xx, xx	x
	[PT 1]	x	x.x	x.x, x.x	x	x	x.x	x.x, x.x	x	x	x.x	xx, xx	x	x	x.x	xx, xx	x	x	x.x	xx, xx	x
	[PT 2]	x	x.x	x.x, x.x	x	x	x.x	x.x, x.x	x	x	x.x	xx, xx	x	x	x.x	xx, xx	x	x	x.x	xx, xx	x
[SOC 2]	Any PT	x	x.x	x.x, x.x	x	x	x.x	x.x, x.x	x	x	x.x	xx, xx	x	x	x.x	xx, xx	x	x	x.x	xx, xx	x
	[PT 1]	x	x.x	x.x, x.x	x	x	x.x	x.x, x.x	x	x	x.x	xx, xx	x	x	x.x	xx, xx	x	x	x.x	xx, xx	x
	[PT 2]	x	x.x	x.x, x.x	x	x	x.x	x.x, x.x	x	x	x.x	xx, xx	x	x	x.x	xx, xx	x	x	x.x	xx, xx	x
Adverse Events of Special Interest																					
Any SOC	Any PT	x	x.x	x.x, x.x	x	x	x.x	x.x, x.x	x	x	x.x	xx, xx	x	x	x.x	xx, xx	x	x	x.x	xx, xx	x
[SOC 1]	Any PT	x	x.x	x.x, x.x	x	x	x.x	x.x, x.x	x	x	x.x	xx, xx	x	x	x.x	xx, xx	x	x	x.x	xx, xx	x
	[PT 1]	x	x.x	x.x, x.x	x	x	x.x	x.x, x.x	x	x	x.x	xx, xx	x	x	x.x	xx, xx	x	x	x.x	xx, xx	x
	[PT 2]	x	x.x	x.x, x.x	x	x	x.x	x.x, x.x	x	x	x.x	xx, xx	x	x	x.x	xx, xx	x	x	x.x	xx, xx	x
[SOC 2]	Any PT	x	x.x	x.x, x.x	x	x	x.x	x.x, x.x	x	x	x.x	xx, xx	x	x	x.x	xx, xx	x	x	x.x	xx, xx	x
	[PT 1]	x	x.x	x.x, x.x	x	x	x.x	x.x, x.x	x	x	x.x	xx, xx	x	x	x.x	xx, xx	x	x	x.x	xx, xx	x
	[PT 2]	x	x.x	x.x, x.x	x	x	x.x	x.x, x.x	x	x	x.x	xx, xx	x	x	x.x	xx, xx	x	x	x.x	xx, xx	x
Other Non-Serious Unsolicited Adverse Events																					
Any SOC	Any PT	x	x.x	x.x, x.x	x	x	x.x	x.x, x.x	x	x	x.x	xx, xx	x	x	x.x	xx, xx	x	x	x.x	xx, xx	x
[SOC 1]	Any PT	x	x.x	x.x, x.x	x	x	x.x	x.x, x.x	x	x	x.x	xx, xx	x	x	x.x	xx, xx	x	x	x.x	xx, xx	x
	[PT 1]	x	x.x	x.x, x.x	x	x	x.x	x.x, x.x	x	x	x.x	xx, xx	x	x	x.x	xx, xx	x	x	x.x	xx, xx	x
	[PT 2]	x	x.x	x.x, x.x	x	x	x.x	x.x, x.x	x	x	x.x	xx, xx	x	x	x.x	xx, xx	x	x	x.x	xx, xx	x
[SOC 2]	Any PT	x	x.x	x.x, x.x	x	x	x.x	x.x, x.x	x	x	x.x	xx, xx	x	x	x.x	xx, xx	x	x	x.x	xx, xx	x
	[PT 1]	x	x.x	x.x, x.x	x	x	x.x	x.x, x.x	x	x	x.x	xx, xx	x	x	x.x	xx, xx	x	x	x.x	xx, xx	x
	[PT 2]	x	x.x	x.x, x.x	x	x	x.x	x.x, x.x	x	x	x.x	xx, xx	x	x	x.x	xx, xx	x	x	x.x	xx, xx	x
Note: N = Number of participants in the Safety Population; n = Number of participants reporting each SOC/PT. A participant is only counted once per PT.																					

Tables with similar format:

Table 23: Summary of Unsolicited Adverse Events by MedDRA System Organ Class and Preferred Term, and Vaccination Group, Male Participants

Table 24: Summary of Unsolicited Adverse Events by MedDRA System Organ Class and Preferred Term, and Vaccination Group, Female Participants

Table 25: Number and Percentage of Participants Experiencing Unsolicited Adverse Events by MedDRA® System Organ Class and Preferred Term, Maximum Severity, Relationship, and Vaccination Group

MedDRA® System Organ Class	MedDRA® Preferred Term	Any Incidence		Severity ¹				Relationship to Treatment ²					
				Mild		Moderate		Severe		Not Related		Related	
		n	%	n	%	n	%	n	%	n	%	n	%
Full IHV01/A244 (N=X)													
Any SOC	Any PT	x	xx	x	xx	x	xx	x	xx	x	xx	x	xx
[SOC 1]	Any PT												
	[PT 1]												
	[PT 2]												
[SOC 2]	Any PT												
	[PT 1]												
	[PT 2]												
Fractional IHV01/A244 (N=X)													
[repeat for all groups]													
Note: N = Number of participants in the Safety Population.													
¹ For severity, a participant is counted once per preferred term and is summarized according to the highest reported severity.													
² For relationship, a participant is only counted once per preferred term and is summarized according to the closest reported relationship.													

Table 26: Number and Percentage of Participants Experiencing Unsolicited Adverse Events Within 28 Days of Study Vaccination, by MedDRA® System Organ Class and Preferred Term, Maximum Severity, Relationship, and Vaccination Group

MedDRA® System Organ Class	MedDRA® Preferred Term	Any Incidence	Severity ¹				Relationship to Treatment ²							
			Mild		Moderate		Severe		Not Related		Related			
			n	%	n	%	n	%	n	%	n	%	n	%
Full IHV01/A244 (N=X)														
Any SOC	Any PT		x	xx	x	xx	x	xx	x	xx	x	xx	x	xx
[SOC 1]	Any PT													
	[PT 1]													
	[PT 2]													
[SOC 2]	Any PT													
	[PT 1]													
	[PT 2]													
Fractional IHV01/A244 (N=X)														
[repeat for all groups]														
Note: N = Number of participants in the Safety Population.														
¹ For severity, a participant is counted once per preferred term and is summarized according to the highest reported severity.														
² For relationship, a participant is only counted once per preferred term and is summarized according to the closest reported relationship.														

Table 27: Summary of Laboratory Results by Parameter, Maximum Severity, Visit, and Vaccination Group – [Parameter]

Visit	Vaccination Group	N	None		Mild / Grade 1		Moderate/ Grade 2		Severe/ Grade 3		Missing	
			n	%	n	%	n	%	n	%	n	%
Baseline (Day 0)	Full IHV01/A244	x	x	x.x	x	x.x	x	x.x	x	x.x	x	x.x
	Fractional IHV01/A244	x	x	x.x	x	x.x	x	x.x	x	x.x	x	x.x
	Full IHV01/A244 + ALFQ	x	x	x.x	x	x.x	x	x.x	x	x.x	x	x.x
	Fractional IHV01/A244 + ALFQ	x	x	x.x	x	x.x	x	x.x	x	x.x	x	x.x
	Placebo	x	x	x.x	x	x.x	x	x.x	x	x.x	x	x.x
